In this open-label Phase 1b study, eligible participants with early or mild Alzheimer's disease (AD) will be randomized 6:2 to receive phenserine or donepezil for a total treatment duration of 8 weeks. Participants will dose escalate at 2- to 4-week intervals (depending on their treatment assignment) to achieve a maintenance dose level that is well tolerated. The objectives of the study are to characterize phenserine's pharmacodynamic activity in comparison to donepezil as evaluated by changes in exosome biomarkers and effects on cognition. In addition, safety, tolerability and pharmacokinetic assessments will be evaluated. The data from the study will be used to select an appropriate dose range for a subsequent Phase 2 proof-of-concept study to characterize phenserine's efficacy and safety in people with early or mild Alzheimer's Disease (AD) over a longer treatment duration.

The protocol is further summarized in the following synopsis and in the study schema that is presented in Figure 1. In addition, a detailed Schedule of Activities is presented in Table 1.

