1.3. Schedule of Activities (SoA)**Table 1. Schedule of Activities**

	Screening (within 28 days before baseline)	Treatment Period					Safety Follow-up ¹ /EOS (within 28 days after last visit)
		Baseline	W2	W4	W6	W8	
Days \pm Visit window	-28 to 0	0	(14\pm 3)	(28\pm 3)	(42\pm 3)	(56\pm 3)	(56\pm 28)
Informed consent	X						
Demographics	X						
Medical history ²	X						
Concomitant medications	X	X	X	X	X	X	X
Vital signs	X	X	X	X	X	X	X
Physical Exam	X	X	X	X	X	X	X
Neurological Exam	X						X
ECG	X	X	X	X	X	X	X
MMSE	X						
MoCA		X				X	
CDR	X						
MRI ³	X						
Suicidal screening using C-SSRS, modified ⁴	X			X		X	X
Inclusion/Exclusion criteria	X	X					
Randomization		X					
Dispense of IMP ⁵		X	X	X	X		
Adverse events		X	X	X	X	X	
AchE sample collection		X	X	X	X	X	

Dose review (for escalation or de-escalation)			X	X	X		
Exosome Biomarker Collection		X	X	X	X	X	
Blood and CSF-based biomarkers ⁶	X					X ⁷	
PK sample collection			X	X	X	X	
Safety laboratory test ⁸	X		X	X	X	X	X
Urinalysis	X		X	X	X	X	X
FSH test ⁹	X						
Pregnancy test ¹⁰	X		X		X		
FLAME Cognitive battery		X				X	

¹ A safety follow-up visit will be conducted within ~4-weeks after the last study-drug dose for all participants who complete the study or who terminate early.

² Includes prior medication use.

³ Only if no MRI scan available within last 2 years.

⁴ The C-SSRS will only be conducted at the follow-up/EOS visit, if the patient experienced suicidal thoughts after the study treatment period.

⁵ Before any dose escalation. According to tolerability and laboratory tests, the dosage will be reassessed, and participants may need to return to the center for a reduced dose.

⁶ CSF samples will only be collected from patients who specifically consent to CSF sample collection and analysis. If CSF biomarker data are available then there is no need for a new CSF collection at screening

⁷ CSF collection at W8 is voluntary and requires an additional informed consent.

⁸ Renal and liver function will be taken every visit. Full Safety laboratory battery will be taken at screening and safety follow-up.

⁹ Women considered post-menopausal will have an FSH test to confirm their status during the screening period and prior to dosing.

¹⁰ Pregnancy testing is required for all women of childbearing potential within one day prior to receiving the first dose of study drug.

2. Introduction

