4.4.3. Study Partner Role in Compliance

Due to the varying dosing schedules during titration, study partners are asked to support participant compliance by:

- Reminding participants of scheduled doses.
- Monitoring and reporting any side effects.
- Assisting in documenting any missed or delayed doses in the subject diary.

The study partner will be instructed by the study personnel at site on how to support the participant in completing the subject diary and how they can be supportive in terms of compliance.

4.4.4. Dose escalation:

Based on tolerability, including adverse events and laboratory testing, the study clinician will decide whether the dose will be escalated as per the study plan. If clinical tolerability is deemed acceptable, the participant will receive the next dose level. If not the previous dosing regime will be continued. The detailed handling of this situation is outlined in a dedicated SOP.

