6.6. Dose Modification

As shown in the Study Schema (Figure 1), participants randomized to the phenserine arm will initiate dosing at 5 mg bd and maintain this dose for the first two weeks of study treatment. At the Week 3 visit, participants may be escalated to 10 mg bd, then 10mg tds (Figure 1), based on tolerability, including adverse events, clinical assessment, ECG and safety laboratory measurements. Participants who are unable to tolerate a higher dose will have their dose reduced to the next previous dose level and maintained at that dose through the remainder of the study. This clinical decision will be made by the study physician and the study team at each centre at the visit, or when any safety laboratory results are received during the days after the visit. If needed, the medical monitor and the PI will be contacted. All participants are expected to be at their individualized maintenance dose for 4 weeks (beginning of Week 5 through the end of Week 8).

Participants randomized to the donepezil arm, will initiate dosing at 5 mg od and will be evaluated at the Week 4 visit for dose escalation to 10 mg once daily. For participants in the phenserine arm, dosing will follow a stepwise escalation to ensure safety and efficacy:

- **Weeks 1-2:** Participants will begin with 5 mg twice daily (bd).
- **Weeks 3-4:** Participants will escalate to 10 mg twice daily (bd) if the initial dose is well tolerated.
- **Weeks 5-8:** Participants will further escalate to 10 mg three times daily (tds) based on continued tolerability.

Before any dose escalation, the dosage will be reassessed based on tolerability. If necessary, participants may be required to return to the center for a dose reduction. Throughout the study, dose adjustments will be made according to tolerability. Should any dose escalation lead to adverse effects that compromise the participant's well-being or safety, the dose will be reduced to the previously well-tolerated level. Participants will then continue at this adjusted dose for the remainder of the study period. These procedures are outlined in more detail in the dedicated SOP.

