3.4 Adherence and Protocol Deviations

3.4.1 Adherence to Allocated Treatment

Adherence to the allocated study treatment will be assessed for all participants who receive at least one dose of investigational medicinal product (IMP). Adherence is defined as the extent to which participants take the study medication according to the prescribed dosing regimen.

Compliance will be assessed using capsule counts and subject diaries and will be calculated as:

$$\% \text{ Compliance} = \left(\frac{\text{Number of capsules taken}}{\text{Number of capsules prescribed}} \right) \times 100$$

The number of capsules prescribed will be calculated based on the duration of treatment (date of last dose – date of first dose + 1) multiplied by the number of capsules prescribed per day according to the assigned dose level.

Compliance will be summarized by treatment group and overall. Participants will be classified as compliant if their calculated compliance is within 80–120% of the prescribed dosing, in accordance with the protocol definition.

The following summaries will be presented:

- Mean, median, and range of percentage compliance
- Number and percentage of participants classified as compliant
- Number and percentage of participants with compliance <80% or >120%

Compliance summaries will be descriptive only and no formal statistical comparisons will be performed.

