8.1 Safety and Tolerability

Summarized by treatment arm:

- Incidence of AEs and SAEs
- GI AEs of special interest
- Laboratory abnormalities

- ECG changes
- Dose reductions and discontinuations

AEs will be coded using MedDRA.

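### SAP 8.1 does not tabulate withheld or capped escalations or the dose level participants reached, and it omits the protocol's safety summary by dose level

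*SAP*

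**What the plan says.** SAP 8.1 gives five items, all "Summarized by treatment arm": AEs and SAEs, "GI AEs of special interest", laboratory abnormalities, ECG changes, and "Dose reductions and discontinuations". Dose level is not a stratum.

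The protocol describes three ways in which a phenserine participant who stays on treatment can end below 10 mg tds:

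- **Reduction after a failed escalation (6.6).** "Participants who are unable to tolerate a higher dose will have their dose reduced to the next previous dose level". SAP 8.1 counts this.
- **Escalation withheld (4.4.4).** The clinician judges tolerability before each step. "If not the previous dosing regime will be continued".
- **Study-level cap (2.3.1).** If more than 2 participants have dose-limiting side effects at 10 mg tds, later participants may go no higher than 10 mg bd.

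The Schedule of Activities has a row at Weeks 2, 4 and 6 that begins "Dose review (for escalation or de-escalation".

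On purpose, the Protocol Summary states: "The data from the study will be used to select an appropriate dose range for a subsequent Phase 2 proof-of-concept study". Protocol 3.2.2 says phenserine is escalated to a maximum tolerated dose, and that tolerability is assessed primarily from AEs related to cholinesterase inhibition. Protocol 10.3 plans standard safety data by arm and dose level. Protocol Table 2 stratifies achievement of the AChE target by dosing regimen.

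**The concern.** In a titration trial, the number of participants who reach each level and can stay there is a direct description of tolerability. Under this protocol, one response to poor tolerability at a dose review is simply not to escalate. That leaves no trace in a count of reductions and discontinuations. A capped participant leaves none either.

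Followed exactly, SAP 8.1 could therefore report few or no dose modifications on phenserine although a sizeable share never reached the planned maintenance dose. Without the dose-level stratum, a reader could not relate the AEs to the doses at which they occurred. Those choosing the Phase 2 dose range would have to rebuild both from listings.

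**Working it through.** The plan states no figure on this point. The check compares what each SAP output would show, then illustrates the size.

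**1. Three phenserine profiles.** Inputs: the schedule in Protocol Table 3 (5 mg bd for Weeks 1-2, 10 mg bd for Weeks 3-4, 10 mg tds for Weeks 5-8), taken as 56 dosing days with every assigned capsule swallowed.

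| Profile | mg received | Share of plan | Capsules | Reductions or discontinuations |
|---|---|---|---|---|
| Full schedule | 14×10 + 14×20 + 28×30 = 1,260 | 100% | 28 + 28 + 84 = 140 | 0 |
| Held at 10 mg bd | 14×10 + 42×20 = 980 | 78% | 28 + 84 = 112 | 0 |
| Held at 5 mg bd | 56×10 = 560 | 44% | 56×2 = 112 | 0 |

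The dose-modification line does not distinguish the three.

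**2. Does compliance distinguish them?** The denominator in SAP 3.4.1 is treatment duration "multiplied by the number of capsules prescribed per day according to the assigned dose level". Read as the level actually assigned, compliance is 140/140, 112/112 and 112/112, so 100% each time. Read as the planned schedule, both held profiles give 112/140 = 80%, which is still inside the 80-120% window, because the formula counts capsules and not milligrams. Measuring compliance against the assigned dose is in line with the protocol and is not itself a fault. It just cannot stand in for dose reached.

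**3. Does any other output?**

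- The outcome overview in SAP 4.5 has no dose item.
- SAP 8.3 gives the proportion reaching the AChE target, the time to reach it and the duration above it, with no dose stratum written. SAP 2.3 adopts the endpoint definitions of Protocol Section 3 and Table 2, so stratification by regimen arguably carries over for that endpoint. It uses dose as a stratum, not as a result.
- The safety summary by dose level is in Protocol 10.3, outside the section that SAP 2.3 adopts.
- SAP 3.4.2 treats a dose inconsistent with the escalation rules as a major deviation. A hold follows the rules, so it is not recorded there.

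**4. Size, for illustration.** The hold rate is an assumption. Suppose k of 12 phenserine participants are held below 10 mg tds and none is reduced or stopped. The line in SAP 8.1 shows 0/12, with an exact (Clopper-Pearson) 95% CI of 0% to 26.5%. A table of dose reached would show:

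| k | Not reaching 10 mg tds | Exact 95% CI |
|---|---|---|
| 1 | 8.3% | 0.2% to 38.5% |
| 2 | 16.7% | 2.1% to 48.4% |
| 3 | 25.0% | 5.5% to 57.2% |
| 4 | 33.3% | 9.9% to 65.1% |
| 6 | 50.0% | 21.1% to 78.9% |

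If each participant independently has probability p of a withheld escalation, the chance of at least one among 12 is 1 − (1 − p)^12. This is 72%, 93% and 99% for p = 0.10, 0.20 and 0.30. Even a modest rate would probably produce a case.

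**The case against.** The strongest reply is that the plan does not ignore intolerance. Four of the five items in SAP 8.1 concern AEs, laboratory findings and ECGs, and Protocol 3.2.2 makes AEs related to cholinesterase inhibition the main tolerability measure. Escalation decisions rest on that same information, so the event behind a hold would be counted. This stands. A reader might infer that tolerability is measured only by reductions and discontinuations, or that a held participant contributes no event at all. The documents do not support either reading: the omission is confined to the dose-modification line. Even so, an AE count by arm does not show which event stopped an escalation, at what dose, or how many participants stayed at each level.

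A second reply is that the protocol does use dose level, in 10.3 and in Table 2, so it would be wrong to say that dose is never analysed. This also stands. The gap is that the SAP does not carry the safety stratum through, and that neither document tabulates dose reached.

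Third, dose reached is not a listed endpoint, and Phase 2 dose selection is to draw on PD, PK and safety data together. That is a reason to add a descriptive table under 8.1, not a new outcome.

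A reader might also infer that the reduction count is unfair between arms, since planned time above the starting dose is 42 of 56 days on phenserine and 28 of 56 on donepezil. The days are right. But more reductions under equal tolerability would follow only if the daily risk were also equal. With 4 donepezil participants and no formal testing, the point carries little weight.

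**Conclusion.** The point holds as a gap in reporting. SAP 8.1 omits the dose-level stratum of Protocol 10.3. Its one dose-modification line misses withheld and capped escalations, and no SAP output states how many participants reached and stayed on each level. A phenserine participant could receive 44% of the planned milligrams and look the same as a full escalator on both that line and compliance.

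The profiles and the capsule arithmetic follow from the protocol's schedule. How many participants would be affected cannot be known from the documents: every hold rate above is assumed, and the chances of at least one hold also assume independence between participants. The cap would add to the number below the top dose, but the participants who triggered it would normally appear as reductions, discontinuations or AEs.

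The consequence is that dose intolerance may be understated in a 16-person exploratory study whose analyses are descriptive. It does not affect the primary biomarker comparison. The change is worth making because it is cheap and bears on the trial's stated purpose.

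**What to change.** Keep the existing line in SAP 8.1 and add the following for the Safety Analysis Set, by arm and descriptive only:

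- **Dose reached.** Number and percentage, with exact 95% CI, reaching each dose level; dose level at Week 8; days on each level.
- **Outcome of each planned escalation decision** (phenserine Weeks 2 and 4, donepezil Week 4). Number escalated, withheld for tolerability, not escalated because of the study-level cap, and not escalated for another reason (including an earlier reduction). The denominator is the number reaching that decision, with those already stopped shown separately so that every participant is accounted for.
- **Listing.** All reductions and discontinuations whenever they occur, including between visits and after Week 6, with dose level and reason.

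Report withheld-for-tolerability alongside reductions and discontinuations as a dose-intolerance outcome. Keep the cap separate, because it does not reflect the participant's own tolerability. Restore the safety summaries by dose level, and state how an event is assigned to a level.

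The cost is one or two tables. Dose reviews are already scheduled, and Protocol 6.5 records dispensed quantities and the dates of delays and reductions. The reason for withholding an escalation is not clearly among the recorded items and may need one eCRF field. Phenserine may look less well tolerated than under the current line. No dosing rule changes.

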8.2 Pharmacokinetics

- Summary of plasma concentrations at steady state
- PK parameters (C_{max}, T_{max}, AUC if derivable)
- Graphical exposure–response plots versus:
 - AChE inhibition
 - Key exosome markers

8.3 AChE Inhibition

- Proportion achieving $\geq 45\%$ inhibition
- Time to reach target inhibition
- Duration above target threshold

Summarized descriptively and graphically.

8.4 Compliance

- Percentage of prescribed doses taken
- Proportion within 80–120% compliance window

9 Exploratory Analyses

9.1 CSF and Plasma Biomarkers

- Change from baseline at Week 8
- Descriptive summaries only
- Correlation analyses with exosome biomarkers (Spearman)

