To evaluate disease modification by assessing changes in specific biomarkers of Alzheimer's Disease (AD) in cerebrospinal fluid (CSF): A β 1-40, A β 1-42, Tau, and p-tau, and in blood plasma: p-tau217 and Nfl.	Assess changes in Alzheimer's Disease (AD) biomarkers in cerebrospinal fluid (CSF): A β 1-40, A β 1-42, Tau, and p-tau, and in blood plasma: p-tau217 and Nfl.
To assess phenserine's potential short-term effects on specific cognitive tasks using the FLAME Memory Composite and other cognitive sub-tests	Neuropsychology assessments will be conducted using the FLAME computer-based domain composites for memory, executive function, attention and sustained attention to evaluate changes over the 8-week treatment period in the phenserine treated participants compared to those who received donepezil.
To assess effect on global cognition	The Montreal Cognitive Assessment (MoCA) will be administered at baseline and at the end of the study to evaluate changes in overall cognitive function across multiple domains, including visuospatial abilities, language, attention, memory, and executive function.

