5.1. Inclusion Criteria

1. A diagnosis of AD based on the most recent NIA-AA diagnostic criteria for AD (27).
2. A significant change on a validated AD amyloid or tau biomarker (as determined either by visual reading of amyloid PET scans [using any of the approved ligands], or CSF A β 1-42 or blood p-tau 217 levels [cut-off as determined by the individual laboratory]).
3. MCI (FDA stage 3) or mild dementia (FDA stage 4) based on a CDR Global rating of 0.5 (MCI) or 1.0 (mild dementia) (28)
4. An MRI scan within the past two years that has no findings inconsistent with AD.
5. Participants who have recently participated in other clinical trials or have been under treatment with memantine or acetylcholinesterase inhibitors (e.g., Donepezil, Rivastigmine, Galantamine) must undergo a washout period of at least 4 weeks prior to the start of the study.
6. Capacity to give informed consent based on the clinical judgement of an experienced clinician.
7. The participant has an individual who is in regular, daily contact via phone or in-person visits and who can act as a reliable study partner and provide meaningful input into rating scales.
8. Age \geq 50 years.
9. Fluency in Norwegian and evidence of adequate premorbid intellectual functioning.
10. Capable of participating in all scheduled evaluations and complete all required tests.
11. Females of childbearing potential and males must commit to use highly effective methods of birth control (see highly effective birth control for male and females described in 11.4 appendix 4) from signing informed consent form until at least 30 days after last administration of phenserine or donepezil.

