9.21. Biomarkers

Blood and CSF biomarker samples will be collected at Screening and Week 8, while exosomal biomarkers will be assessed at Baseline, Week 2, Week 4, Week 6, and Week 8. This comprehensive evaluation of mechanistic biomarkers through exosome technologies aims to deliver a detailed understanding of the impact of phenserine versus donepezil on various facets of AD neuropathology, contributing to the trial's primary objective.

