10.2. Statistical Hypotheses

- **Primary Hypothesis:**

- There is a difference between phenserine and donepezil in terms of their effect on the primary endpoint, which involves changes in exosome biomarkers of pre-programmed cell death, synaptic integrity and function, neuroinflammation, and AD-related protein trafficking.

- **Secondary Hypothesis**

- Phenserine and donepezil do not differ in their safety and tolerability profiles, as measured by the rate and severity of adverse events (AEs).

- **Exploratory Hypothesis:**

- Phenserine has a different effect compared to donepezil on short-term cognitive performance, as measured by the FLAME Memory Composite and other cognitive sub-tests.
- Phenserine and donepezil differ in their effects on changes in blood and cerebrospinal fluid (CSF) biomarkers, including A β 1-40, A β 1-42, Tau, p-tau, p-tau217, and NfL

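### SAP 9.1 names no between-arm estimate for plasma and CSF markers, although p-tau217 and CSF Aβ1-42 can be both the entry test and the baseline, so within-arm change can drift toward normal without any drug effect

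*SAP*

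**What the plan says.** **Entry.** Protocol 5.1, criterion 2, requires "A significant change on a validated AD amyloid or tau biomarker". Three routes satisfy it: "visual reading of amyloid PET scans", CSF Aβ1-42, or "blood p-tau 217 levels [cut-off as determined by the individual laboratory". No numerical cut-off is given.

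**Sampling.** Protocol 9.21 states: "Blood and CSF biomarker samples will be collected at Screening and Week 8". The Schedule of Activities agrees, with nothing in that row at the baseline visit. Its footnotes let existing CSF data stand in for a screening lumbar puncture and make Week 8 CSF voluntary under a separate consent. SAP 4.5 gives the timeframe for these markers as baseline to Week 8, so the screening value has to serve as baseline.

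**Purpose.** Protocol Table 2 words the objective as "To evaluate disease modification by assessing changes in specific biomarkers". Protocol 10.2 sets the hypothesis: "Phenserine and donepezil differ in their effects on changes in blood and cerebrospinal fluid (CSF) biomarkers".

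**Analysis.** SAP 9.1 lists change from baseline at Week 8, "Descriptive summaries only", and "Correlation analyses with exosome biomarkers (Spearman"). It names no arm contrast, baseline adjustment or interval. SAP 7.2, by contrast, plans between-arm mean change differences with 95% CI for the exosome markers.

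**The concern.** If people are admitted because one noisy measurement crossed a threshold, and change is then counted from that same measurement, the average moves back toward the screened population's mean even when treatment does nothing. A p-tau217 selected for being high drifts down, and a CSF Aβ1-42 selected for being low drifts up. Both look like improvement.

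Randomisation protects against this, because both arms pass the same entry rule, but only if the arms are contrasted. SAP 9.1 leaves that contrast unnamed. A report giving the phenserine arm's change with a confidence interval would comply with the SAP. Table 2 supplies a disease-modification label for such a change, and the protocol says the results will guide doses and outcome measures for Phase 2.

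**Working it through.** **The plan's own figures.** The documents give no expected change, SD or precision for p-tau217, NfL or any CSF marker. The only computable figure is the exosome sample size: 4 per arm for 80% power at 2.45 SD. It reproduces (two-sided t-test power 0.619 at 3 per arm and 0.821 at 4), but it does not bear on this point.

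**Inputs from the documents.** 12 phenserine and 4 donepezil participants; entry possible on p-tau217 or CSF Aβ1-42; one scheduled pre-treatment sample, at screening.

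**Assumptions.**
- r, the correlation between screening and Week 8 values without a drug effect: 0.7 to 0.95.
- c, the cut-off in SD from the mean of those screened, signed so that abnormal is high: −1 to +1. This corresponds to 84% down to 16% of those tested passing.
- Values are bivariate normal with equal variance at both times.
- All 12 phenserine participants qualified on this marker's screening sample.

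**Step 1: shift under no effect.** With λ = φ(c)/(1 − Φ(c)), the mean change is −(1 − r)λ, in SD of the marker. At c = 0, λ = 0.798, so r = 0.9 gives 0.1 × 0.798 = 0.080 and r = 0.7 gives 0.3 × 0.798 = 0.239.

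**Step 2: chance that a within-arm 95% CI excludes zero.** The variance of the selected screening value is v = 1 − λ(λ − c). The SD of change is √[(1 − r)²v + 1 − r²]. At c = 0 and r = 0.9, v = 0.363, the SD is 0.440, and the noncentrality is (0.080/0.440) × √12 = 0.63. On 11 df the two-sided exclusion rate is 8.9%, against a nominal 5%.

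Each cell shows the size of the shift toward normal in SD, then the exclusion rate:

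| r | c = −1 | c = −0.5 | c = 0 | c = +0.5 | c = +1 |
|---|---|---|---|---|---|
| 0.95 | 0.014; 5.2% | 0.025; 5.8% | 0.040; 6.9% | 0.057; 8.9% | 0.076; 12.1% |
| 0.9 | 0.029; 5.5% | 0.051; 6.5% | 0.080; 8.9% | 0.114; 13.1% | 0.153; 19.7% |
| 0.8 | 0.058; 6.0% | 0.102; 8.2% | 0.160; 13.1% | 0.228; 22.1% | 0.305; 35.6% |
| 0.7 | 0.086; 6.5% | 0.153; 10.0% | 0.239; 17.7% | 0.342; 31.7% | 0.458; 51.2% |

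**Step 3: dilution.** The mean shift scales with the share of the arm that qualified on this marker's own baseline sample. If that share is half, with the SD of change unchanged, c = 0 and r = 0.8 to 0.9 give 0.040 to 0.080 SD and exclusion rates of 6% to 7%.

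**Step 4: the arm contrast.** In simulated trials with no drug effect at 12 v 4 (c from −0.5 to +0.5, r from 0.7 to 0.95), the mean phenserine-minus-donepezil difference in change lay between −0.004 and +0.004 SD. Its 95% CI excluded zero in 4.7% to 5.2% of trials. The contrast removes the artefact.

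**Step 5: precision of the contrast.** At 12 v 4 the standard error is √(1/12 + 1/4) = 0.577 residual SD. With one covariate there are 13 df, so the half-width is 2.160 × 0.577 = 1.25 residual SD. If CSF pairs came from 6 v 2 (assumption), an unadjusted comparison gives 2.447 × √(1/6 + 1/2) = 2.0 SD of change on 6 df. A covariate-adjusted one gives about 2.1 residual SD on 5 df.

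**The case against.** **Not every marker is exposed.** A reader might infer that the whole of SAP 9.1 is affected. Criterion 2 does not support that: four of the six markers in Table 2 (NfL, CSF Aβ1-40, tau and p-tau) cannot qualify anyone, so they have no direct selection effect. This stands. The missing contrast still leaves the Protocol 10.2 hypothesis without an estimate for any of the six.

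**Not every participant is selected on the baseline value.** PET is a full alternative route, and someone admitted on CSF is not selected on p-tau217. An earlier CSF result followed by a fresh pre-treatment draw also avoids the problem, although reusing the earlier qualifying result as baseline would not. Screening is in memory clinics with a required AD diagnosis, so a cut-off below the screened mean is plausible. At r = 0.8 to 0.9 and c = −1 to −0.5, the exclusion rate is only 5.5% to 8.2%. This stands and lowers the likely size.

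**The SAP plans no within-arm test.** A reader might take the exclusion rates for the error rate of a planned analysis. They are not. SAP 5 rules out formal testing, and SAP 2.3.1 has exploratory outcomes interpreted descriptively. The rates show how often a permitted summary would mislead.

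**The comparison is partly implied elsewhere.** SAP 2.3 takes endpoints from Protocol Section 3, where blood markers are to be compared across the groups. SAP 2.3.2 asks for 95% CIs on efficacy estimates. A descriptive analysis can show both arms. All true, but none of this says which estimate SAP 9.1 will report, and a within-arm interval would satisfy it.

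**The contrast is imprecise.** Four donepezil participants cannot resolve a shift of this size, and voluntary CSF may leave no pairs in that arm. This limits the remedy for CSF. It does not make the tighter within-arm figure sound.

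**Conclusion.** The point holds for plasma p-tau217 and CSF Aβ1-42. For these, one screening value can both admit the participant and serve as the only pre-treatment value, and SAP 9.1 does not name the arm difference that would cancel the resulting drift.

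If the whole phenserine arm qualified on the marker, the drift is 0.01 to 0.46 SD and a within-arm 95% CI excludes zero in about 5% to 51% of trials with no drug effect. At correlation 0.8 to 0.9 the rate is 9% to 36% for a cut-off 0 to 1 SD above the screened mean, and 5.5% to 8% for one 0.5 to 1 SD below it. The correlation, the cut-off and the share qualifying by each route are assumptions. With a highly repeatable assay or mostly PET entry the effect is small.

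The documents do not support two stronger conclusions: that descriptive analysis itself creates the bias, or that the randomised comparison is biased. The fault is the unnamed contrast, on an exploratory endpoint.

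**What to change.** In SAP 9.1:

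- For plasma p-tau217 and NfL, report the phenserine-minus-donepezil difference in log Week 8 value, adjusted for the log pre-treatment value, with 95% CI.
- For CSF markers, report the between-arm difference in change where paired samples exist in both arms. Otherwise list individual values.
- State that change within an arm is not evidence of disease modification. Keep the planned change summaries as description.
- In the listings, flag participants who qualified on that marker's own pre-treatment sample. With four donepezil participants this can only be a listing, not a subgroup estimate.

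The cost is a few lines of SAP text and one small model per plasma marker, using data already collected. SAP 1.1 provides for an amendment before database lock. The drawback is a wide interval: a half-width of about 1.25 residual SD at 12 v 4, and wider for voluntary CSF. That is the precision the design can give.
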